### **B. The secondary endpoints** of this study consist of the following:

- a. Blood levels of HbA1c and the lipid-panel analytes (cholesterol, HDL-C, LDL-C, triglycerides).
- b. Plasma hormone levels (Insulin, IGF-I, IGF-II, leptin, and adiponectin).
- c. Plasma-measured expression levels of mRNAs and miRs, measured using quantitative RT-PCR and miR-profiling microarrays, respectively.
- d. Tissue-measured expression levels of mRNAs and miRs, measured using quantitative RT-PCR and miR-profiling microarray, respectively.

## Data Handling and Recordkeeping

The PI will carefully monitor study procedures to protect the safety of research subjects, the quality of the data and the integrity of the study. The data will be kept in an electronic database in the office of clinical trials at the Winthrop P. Rockefeller Cancer Institute. Only the PI and Co-I, CRAs, regulatory personnel, biostatistician and lab personnel performing the analyses will have access to the data. In the event that a subject fails screening, only the eligibility criteria case report form will be completed.

## Monitoring

**Medical Monitor:** The Medical Monitor, Principal Investigator and study staff will meet quarterly, once the PI has monitored the data, to review safety data (adverse events, serious adverse events and other scientific observations).

**Study Monitor:** The study will be monitored to ensure that the rights and well-being of human subjects are protected, that the data are accurate, complete and verifiable from source documents and that the trial is conducted in compliance with currently approved protocol/amendments on a quarterly basis.

## Statistical Considerations

General approach: For each tissue endpoint, the tumor-NTU difference will be calculated in each patient as the paired difference in values between tumor and adjacent NTU tissue. For each blood endpoint, the endpoint response to treatment will be calculated in each patient as the paired difference between post-study and pre-study values. All data will be summarized by treatment arm as the mean, standard deviation (SD), median, and range, and will be graphed as box plots. Tumor-NTU differences and endpoint responses will be compared against zero via signed-rank test within each treatment arm. Treatment arms will be compared to each other for differences via Wilcoxon rank-sum tests, with additional details provided below. All statistical comparisons will be two-sided, and will employ a 10% alpha to reduce Type II error in this pilot proof-of-concept study.

Analysis plan for tolerability: Meformin-related adverse events will be summarized by type and treatment arm, both as proportions at each grade and as average grades (i.e., mean scores). For each type, the Wilcoxon rank-sum test will be used to compare treatment arms for differences in average grade.

Analysis plan for the IHC-based primary endpoints: The IHC-based primary endpoints will be measured in tissue, and will include markers of proliferation (Ki67, phospho-histone H3, ER $\alpha$ , PR, and hTERT), anti-proliferation and apoptosis (PTEN, KLF9, cleaved caspase-3 and TUNEL staining), and insulin-mediated signalling (total and phosphorylated versions of Akt, Erk1/2, AMPK, and receptors for Insulin, IGF-I, and IGF-

II). Endpoints measured in tumor tissue, adjacent NTU tissue, and tumor-NTU differences will be summarized and graphed as described above. Wilcoxon rank-sum tests will be used to compare endpoints measured in tumor, and likewise endpoints measured in adjacent NTU tissue, for differences between the metformin and no-metformin treatment arms.

Analysis plan for secondary endpoints measured in blood or plasma: The secondary endpoints measured in blood will be the levels of HbA1c, cholesterol, HDL-C, LDL-C, and triglycerides. The secondary endpoints measured in plasma will be the plasma hormone levels (Insulin, IGF-I, IGF-II, leptin, and adiponectin) and the plasma-measured expression levels of mRNAs and miRs. Endpoints measured at pre-study and post-study, and endpoint responses to treatment will be summarized and graphed as described above. Wilcoxon rank-sum tests will be used to compare endpoint responses to treatment for differences between the metformin and no-metformin treatment arms.

Analysis plan for secondary endpoints measured in tissue: The secondary endpoints measured in tissue will be the expression levels of mRNAs and miRs. Endpoints measured in tumor tissue, adjacent NTU tissue, and tumor-NTU differences will be summarized and graphed as described above. Wilcoxon rank-sum tests will be used to compare endpoints measured in tumor, and likewise endpoints measured in adjacent NTU tissue, for differences between the metformin and no-metformin treatment arms.

Sample Size and Power: There will be 20 subjects on each treatment arm, yielding a total of 40 subjects. The two-sided Wilcoxon rank-sum test will be used at 10% alpha to compare all endpoints and endpoint responses for differences between the metformin arm and the no-metformin arm. This study will be considered sufficiently powered to meet research objectives if the Wilcoxon rank-sum test has >90% power at 10% alpha to detect a treatment-arm difference of 1.0 SDs or more. Statistical power of the Wilcoxon rank-sum test was calculated using the 2-sample t-test module of PASS 2011 by selecting options corresponding to the worst-case scenario of underlying normal distributions with unknown SDs. Under this worst case scenario, 20 subjects per treatment arm (for a total of 40 subjects) give the two-sided Wilcoxon rank-sum test 91.6% power at 10% alpha to detect a difference of 1.0 SDs between the metformin and no-metformin arms, thereby establishing that this study is sufficiently powered to meet research objectives.

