#### **A. Method of assigning subjects to treatment groups.**

Subjects will be assigned randomly to one of two groups. Group 1 will receive treatment with metformin, while Group 2 will receive no treatment. Subjects assigned to Group 1 will be administered oral metformin at 500 mg twice a day for 14-21 days followed by surgery. These doses are therapeutic, and will permit patients to undergo their surgical therapy within an appropriate time frame.

Subject eligibility will be established before treatment randomization. Once a subject's eligibility is determined, the Research Staff will be notified to implement the randomization process. Randomization will be completed when the Research Staff receives a copy of the signed consent and the physician's orders for study agent to be dispensed.

To minimize imbalance between treatment arms, the randomization procedure will employ a stratified block randomization with randomly chosen blocks of size 2, 4, and 6, and with BMI as the stratification factor. Randomization will be conducted using sealed envelopes located at the Cancer Clinical Trials Office (CCTO). There will be two sets of consecutively numbered envelopes, one set for subjects with BMI from 30 to 39.9 and one set for subject with BMI of 40 or higher. At each randomization, the lowest numbered envelope will be chosen. The Research Staff will open the envelope and assign the subject to the treatment arm based on the contents of the envelope. The appropriate treatment will then be dispensed to the subject.

Methods for ensuring blinding.

Not applicable: this is an open-label study.

Methods for unblinding the study.

Not applicable: this is an open-label study.

Procedure for unblinding in case of medical emergency.

Not applicable: this is an open-label study.

Metformin will be administered to patients (randomized to receive metformin) for a minimum of 14 days and a maximum of 21 days, representing the typical time interval between confirmation of tumor diagnosis and surgical resection. Following surgical resection, any unused study drug will be returned to the physician at the time of the subject's first post-operative visit.

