#### **F. Treatment modifications**

Patients will be monitored for their ability to tolerate the study medication during weekly follow-up telephone calls. If necessary, anti-diarrheal or anti-emetic therapy may be prescribed to ease any discomfort associated with the medicine. If a patient cannot tolerate the study medication and misses two or more doses in a row, they will be withdrawn from the study.

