#### **G. Subject removal**

Any patient who develops a grade 3 or higher gastrointestinal toxicity while on study will be discontinued. Subjects that withdraw from the study or that are withdrawn from the study due to unacceptable toxicity will return all unused study drug at their next scheduled clinic appointment.

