### Study Calendar

Procedure	Pre-study	Study Period					Post-Operative clinic visit / Early Termination f
		Day 1 (Day of first dose)	Day 8			Days 14 -21 (Surgery)	
Eligibility Assessments							
Informed Consent	X						
Inclusion/Exclusion Criteria	X						
Medical History	X						
Study Assessments							
Physical Examination	X	X					
Physical Measurements e	X	X			X		
Demographics h	X						
Vital signs b		X					
Body Mass Index (BMI)	X				X		
Smoking Status	X						
Alcohol Status	X						
Concomitant Medications j	X	X	X k		X		
Adverse Events (AEs)		X	X k		X		
Telephone contact			X k				
Laboratory Test							
CBC Panel c	X				X		
Comprehensive Metabolic Panel	X				X		
Lipid Panel (Cholesterol, HDL-C, LDL-C, Triglycerides) *	X				X		
Urine Pregnancy Test d		X					
HbA1c *	X				X		
Study labs (send to [name] lab) g	X				X		
Clinical Drug Supplies							
Randomize		X					
Dispense study drug		X					
Dispense patient diary		X					
Review of drug diary			X k				
Collect unused study drug							X
Collect subject diary							X
Pathology							
Tumor Stage							X
Tumor Differentiation	X						X
Lymph Node Involvement							X
Tissue Collection (send to [name] lab)	X i				X		

\*Above standard of care (investigational-to be paid for by grant).

a A comprehensive panel will determine the following serum levels for the following: glucose, calcium, albumin, total protein, sodium, potassium, CO2, chloride, BUN, creatinine, ALP, ALT, AST, and total bilirubin (standard of care).

b Temperature, blood pressure, pulse, respiration rate.

c WBC, Platelets, Hb

d Within 7 days of randomization

e Physical measurements to include ECOG, performance status, weight and height (height only)

f Unused drug and diary to be collected during standard of care visit, no other research activities will be performed.

g Insulin, Leptin, Adiponectin, IGF-I and IGF-II

h Age, sex, race, and ethnicity

i If available

j Record concomitant medications that are actively being taken at time of consent till completion of study.

k Subjects receiving Metformin only

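### The between-arm tests of metformin-related adverse events do not compare like with like: only the metformin arm gets interim adverse-event calls, and "related" has no meaning for untreated controls

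*Protocol*

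**What the plan says.** Tolerability is the second primary objective, and metformin-related AEs are primary endpoint (d) under Outcome Measures. Under Statistical Considerations in the Protocol, and identically in the SAP, these events are summarised by type and arm as proportions at each grade and as mean grades. Then: "For each type, the Wilcoxon rank-sum test will be used to compare treatment arms for differences in average grade". The general approach sets a two-sided 10% level for every comparison.

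On AE collection, the Study Calendar marks AEs on Day 1 and at surgery (Days 14–21) without restriction. The Day 8 AE, telephone and concomitant-medication entries carry footnote k: "Subjects receiving Metformin only". Trial Design section F describes the calls: "Patients will be monitored for their ability to tolerate the study medication during weekly follow-up telephone calls".

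Group 2 receives no treatment and there is no placebo. On blinding, Trial Design section A says: "Not applicable: this is an open-label study".

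Neither document defines metformin-related for the endpoint, says who makes the attribution, or says how it applies to a woman who takes no metformin. The relatedness criterion under Adverse Event Reporting governs reports to the review board and does not define the endpoint.

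**The concern.** A rank-sum test between arms is interpretable only if the outcome means the same thing, and is collected in the same way, in both arms. Neither condition holds here.

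- **Meaning.** If metformin-related is a causal judgement, no control event can qualify, and the test only asks whether a handful of metformin subjects had something attributed to the drug. If it means AE types known for metformin, controls can have them, but the protocol does not say so or name the list.
- **Collection.** Over 14–21 days the metformin arm has one or two extra prompted occasions to report an AE. Controls must recall mild, transient events at surgery. This tends towards a result of worse on metformin.

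These per-type tests are the only between-arm tests planned for a primary objective. For the commoner AE types, a p-value below 0.10 could reflect attribution or extra contact rather than the drug.

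**Working it through.** **Inputs from the documents.** 20 subjects per arm; two-sided 10% level; one rank-sum test per AE type. Risks and Benefits gives percentage frequencies on metformin for 17 types: diarrhoea 50%, nausea or vomiting and gas 10–25%, and 14 others 1–10%.

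**Assumptions (no figures in the documents).** Background AE risk; the share of metformin-arm events attributed to the drug; the share of control events captured relative to the metformin arm; any loss of metformin-arm events.

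**The plan's own figure.** The stated power is 91.6% for a 1.0 SD difference. Noncentral t power with the sample size multiplied by the rank-sum efficiency 3/π gives 20 × 3/π = 19.1 per arm and 91.7%; with 19 per arm it gives 91.6%. The figure reproduces. It concerns a normally distributed measurement and says nothing about AE grades.

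**Test statistic.** With an AE present in x₁ metformin and x₂ control subjects (n = 20 each, N = 40, k = x₁ + x₂), the tie-corrected rank-sum statistic is z² = (N − 1)(20x₁ − 20x₂)² / [20 × 20 × k(N − k)].

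**Causal reading: all controls score zero.**

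- 2/20 against 0/20: z² = 39 × 1600 / (400 × 2 × 38) = 2.05, p = 0.152.
- 3/20 against 0/20: z² = 39 × 3600 / (400 × 3 × 37) = 3.16, p = 0.075 (0.080 with continuity correction; 0.076 if the three grades are 1, 1, 2).
- 4/20 against 0/20: p = 0.037.

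The test therefore rejects whenever at least three metformin subjects have an attributed event. Its rejection rate is P(X ≥ 3), with X binomial(20, true risk × share attributed), although true risk is equal in both arms:

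| True risk | All attributed | Half attributed |
|---|---|---|
| 2% | 0.7% | 0.1% |
| 5% | 7.5% | 1.3% |
| 10% | 32% | 7.5% |
| 20% | 79% | 32% |
| 30% | 96% | 60% |

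**Known-type reading: equal true risk, unequal capture.** Sum the two binomial probabilities over all 21 × 21 outcomes with p < 0.10. The entries are total rejection rates:

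| Control capture | 2% risk | 5% | 10% | 20% | 30% | 50% |
|---|---|---|---|---|---|---|
| 100% | 0.9% | 5.6% | 10.3% | 10.3% | 10.5% | 8.4% |
| 90% | 0.8% | 5.3% | 10.3% | 10.7% | 11.2% | 10.0% |
| 75% | 0.7% | 5.0% | 11.0% | 13.2% | 15.4% | 18.5% |
| 50% | 0.7% | 5.1% | 14.2% | 23.5% | 31.2% | 49.1% |

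The total understates the tilt in direction. At 20% risk and 75% capture, 11.1% of trials reject as worse on metformin and 2.1% as worse on control; with full capture it is 5.1% each way. A simulation with grades 1/2/3 in 70/25/5% of events gave 9.9%, 12.9% and 23.3% at 20% risk for 100%, 75% and 50% capture, close to the present/absent values.

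**Possible offset.** Of subjects who cannot tolerate the drug and miss consecutive doses, section F says "they will be withdrawn from the study". Section G says: "Any patient who develops a grade 3 or higher gastrointestinal toxicity while on study will be discontinued". Footnote f says of the post-operative or early-termination visit that "no other research activities will be performed". If some metformin-arm events are lost this way, the bias shrinks or reverses. At 20% risk and 90% control capture, worse on metformin against worse on control is:

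- no loss: 7.0% against 3.7%;
- 10% of metformin-arm events lost: 5.2% against 5.2%;
- 20% lost: 3.7% against 7.2%.

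At 75% capture with 10% lost it is 8.5% against 3.1%.

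**Diarrhoea at the protocol's 50%.** Here a real difference is expected. With an assumed 10% background, the test finds worse on metformin in 90.7% of trials at full capture and 94.6% at 75%. With 20% background the figures are 64.7% and 79.4%.

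**The case against.** The strongest reply has five parts.

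- **Controls are assessed.** Both arms have AE entries on Day 1 and at surgery, and the Protocol Summary says subjects will be monitored for AEs. At 90% capture the inflation is small, and nothing in the documents supports 50%. This stands: the size cannot be derived from the documents. The unequal schedule is nevertheless written into the calendar.
- **Few types are affected.** Fourteen of the 17 are at 1–10%, and at 5% risk or below unequal capture keeps rejection under the nominal 10%. For diarrhoea a true effect is expected. This also stands, and it leaves mainly nausea or vomiting and gas. It does not cover the causal reading.
- **The causal reading is not the natural one.** The plan summarises these events by arm, so known AE types fit better. I agree and treat the causal figures as the worst case. The protocol should still say which is meant.
- **Loss of events is conjecture.** No passage says AEs before withdrawal are discarded. That is correct. The loss scenarios only soften the concern and show that even the direction is not assured.
- **Little depends on these p-values.** There is no decision rule, this is a pilot, and tolerability is mainly a question about the metformin arm. That limits the consequence. It does not make a planned test on a primary endpoint interpretable, and the results are intended for publication and funding applications.

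**Conclusion.** The concern holds and should be fixed. The unequal AE contact and the missing definition are facts of the documents, and following the plan exactly gives a between-arm comparison that is not like with like.

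The size rests on assumptions. Under the better-fitting reading it runs from negligible (90% capture: 10.0–11.2% rejection at risks of 10–50%) to substantial (50% capture: 14–49%). Under the causal reading, with every event attributed, rejection reaches 32–96% at risks of 10–30%. The net direction under the better-fitting reading is probably, but not certainly, against metformin.

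What is lost is the meaning of the between-arm p-values for the commoner AE types. The metformin-arm proportions are unaffected and can still answer the tolerability objective.

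**What to change.** Choose one of three, in both the Protocol and the SAP.

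(a) **Drop the between-arm test on attributed events.** Report metformin-related AEs and discontinuations in the metformin arm only, as proportions with exact confidence intervals. For example, 3/20 has a 90% interval of 4.2–34.4%, and 0/20 has an upper limit of 13.9%.

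(b) **Keep a comparison, but make it fair.**

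- Use all AEs of pre-specified types regardless of attribution, and state the list once. The Study Drug and Risks and Benefits sections need reconciling: nausea or vomiting appears only in the latter, and weakness is above 10% in one and 1–10% in the other.
- Give controls the same interim AE call or calls and checklist. The diary can stay metformin-only.
- Count onset from the first dose in the metformin arm, including later on the day the calendar labels "Day 1 (Day of first dose", and from randomisation on Day 1 in controls.
- Include AEs up to withdrawal, and the AE that led to it, for all randomised subjects.
- State that open-label reporting bias remains, and that many types are each tested at 10%. With 17 independent types, equal risks and full capture, at least one p < 0.10 occurs in 68% of trials (three types at an assumed 20% risk, 14 at 5%), or 37% if the 14 are at 2%.

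(c) **Describe AEs by arm without p-values**, and state the unequal contact.

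Options (a) and (c) need wording only and give up a p-value that cannot be interpreted. Option (b) adds one or two short calls to each of about 20 controls, 20–40 calls in all, by existing staff.

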## Protocol Summary

This is a randomized, open-label clinical investigation of the effects of short-term oral metformin therapy on biomarkers for tumor growth in subjects with endometrial cancer. Metformin is a well-tolerated drug widely prescribed for treatment of Type 2 diabetes mellitus and for treatment of Polycystic Ovarian Syndrome (PCOS) in non-diabetic women. Clinical trials are ongoing to explore this possibility in breast cancer (NCT01101438). This investigation is the first study of metformin in endometrial cancer patients, and is designed to understand the mechanism of its anti-cancer actions, if any, and its interactions with biomarkers in endometrial cancer patients.

Forty non-diabetic subjects will be randomized so that 20 will receive oral metformin for 14-21 days and the remaining 20 will receive no metformin for 14-21 days. Subjects will be monitored for adverse events (AEs). All subjects will have blood samples collected on Day 1 (prior to start of metformin for subjects randomized to metformin) and prior to surgery. These samples will undergo metabolic, lipid and tumor-specific biomarker analyses. Tumor and adjacent normal tissue taken from subjects from the diagnosis and at the time of surgery will be analyzed for cellular proliferation, apoptosis and biomarker levels.

The **Primary objectives** of this study are as follows:

1. To determine the effect of metformin on tissue markers of proliferation, apoptosis, and insulin-mediated signaling in endometrial cancer in non-diabetic obese women.
2. To determine the tolerability of a short course of metformin in non-diabetic obese women with newly diagnosed endometrial cancer.

The **Secondary objectives** of this study are as follows:

1. To determine the effect of metformin on HbA1c and blood lipid profiles measured at baseline and just before surgery.
2. To determine the effect of metformin on the following hormones measured in blood plasma at baseline and just before surgery: Insulin, IGF-I, leptin, and adiponectin.
3. To determine the effect of metformin on the expression levels of mRNAs and miRs measured in blood plasma at baseline and just before surgery.
4. To determine the effect of metformin on the expression levels of mRNAs and miRs measured in tumor and adjacent non-tumoral uterine tissue.

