### **D. Subject Data**

Subject data to be obtained and recorded will consist of the following:

- a) Patient characteristics: gender; age; BMI; race and ethnicity; smoking status (including approximate packs per day for current and former smokers); alcohol intake.
- b) Tumor characteristics: tumor stage; tumor differentiation status (well, moderate, poor); lymph node involvement; depth of invasion; tumor margins.
- c) Comprehensive metabolic panel: glucose, calcium, albumin, total protein, sodium, potassium, CO2, chloride, BUN, creatinine, ALP, ALT, AST and bilirubin.
- d) Lipid panel: cholesterol, HDL-C, LDL-C, triglycerides.
- e) Plasma markers: plasma HbA1c; plasma insulin; plasma leptin; plasma adiponectin; plasma IGF-I; plasma IGF-II; plasma profiles of miR and mRNA.

- f) Tissue markers: endometrial cancer and uterine apoptotic indices; endometrial cancer and uterine proliferative indices; endometrial tumor miR and mRNA profiles; endometrial (adjacent NTU) miR and mRNA profiles.

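### The primary between-arm test for tumour markers uses neither pre-study grade nor the BMI stratum: it is valid, but may lose power and leaves chance grade imbalance in the result

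*Protocol*

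**What the plan says.** Under Statistical Considerations (analysis plan for the IHC-based primary endpoints), the Protocol says that "Wilcoxon rank-sum tests will be used to compare endpoints measured in tumor, and likewise endpoints measured in adjacent NTU tissue", between the two arms. The SAP repeats the sentence. "All statistical comparisons will be two-sided", and the plan "will employ a 10% alpha to reduce Type II error in this pilot proof-of-concept study". The sample size text says "There will be 20 subjects on each treatment arm, yielding a total of 40 subjects" and requires more than 90% power to "detect a treatment-arm difference of 1.0 SDs or more"; it reports 91.6%.

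The baseline information available is as follows.

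- **Grade.** Inclusion criterion 1 requires histologically confirmed grade I or II disease, so grade is known before randomisation for every patient. Section D (Subject Data) lists differentiation among the items to record. The Study Calendar marks "Tumor Differentiation" both pre-study and at the post-operative visit, and does not attach to it the availability footnote that it attaches to pre-study tissue.
- **BMI.** Section A of Trial Design stratifies randomisation by BMI (30 to 39.9, and 40 or higher). Grade is not a stratification factor.
- **Diagnosis tissue.** The Protocol Summary says "Tumor and adjacent normal tissue taken from subjects from the diagnosis and at the time of surgery will be analyzed", but the calendar collects pre-study tissue only where it exists, and no planned analysis uses a pre-treatment tissue value.

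Blood endpoints, by contrast, are analysed as post-minus-pre change.

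**The concern.** The primary tissue endpoints use less baseline information than the secondary blood endpoints. Grade is balanced neither by the randomisation nor in the analysis. If a marker such as Ki67 differs between grade 1 and grade 2 tumours, two things follow. The variation due to grade stays in the error term, which costs power. And if the arms happen to differ in grade, that difference is carried into the treatment comparison. With 20 patients per arm, a difference of several patients is not rare. The data that would address both are already being collected.

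**Working it through.** **Inputs from the documents.** 20 patients per arm, two-sided 10% alpha, difference 1.0 SD, stated power 91.6%, no covariates.

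**Assumptions (not in the documents).** The share of marker variance explained by grade, R², runs from 0 to 0.30. The share of grade 2 patients, p, is 30% to 50% (20% is also shown for imbalance). The marker is normally distributed, and its total SD, including the part due to grade, is 1.

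**Step 1: reproduce the stated power.** Under normality the rank-sum test has efficiency 3/π relative to the t-test, so the effective n per arm is 20 × 3/π = 19.1, or 19 rounded down. With n = 19 the noncentrality is 1.0 × √(19/2) = 3.08 on 36 degrees of freedom, and power is 91.60%. With n = 19.1 it is 91.7%. Direct simulation of the rank-sum test (40,000 trials per setting) gives 91.2-91.8%. The plan's figure is correct.

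**Step 2: power after adjustment.** Adjusting for grade divides the residual SD by 1/√(1 − R²), so the standardised difference rises from 1.0 to 1/√0.9 = 1.05, 1/√0.8 = 1.12 and 1/√0.7 = 1.20 for R² of 0.10, 0.20 and 0.30. In sample-size terms, 40 patients do the work of 40/(1 − R²) = 44.4, 50.0 and 57.1. The simulated results for an ordinary regression of the ranks on arm and grade are:

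| R² | 1.0 SD, unadjusted | 1.0 SD, adjusted | 0.8 SD, unadjusted | 0.8 SD, adjusted |
|---|---|---|---|---|
| 0 | about 91.6% | 90.8-91.0% | about 77% | not tabulated |
| 0.05 | about 91.6% | 91.9-92.1% | about 77% | not tabulated |
| 0.10 | about 91% | 93.0% | about 77% | 80-81% |
| 0.20 | about 91% | 95.2-95.3% | about 77% | 84-85% |
| 0.30 | about 91% | 96.9% | about 77% | 88% |

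Adding the BMI stratum as a second term leaves these figures essentially unchanged when BMI is not prognostic. Break-even is at an R² of about 0.03-0.05. Overall type I error stays near 10% for both tests.

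**Step 3: how often grade is unbalanced.** Take the grade 2 counts in the two arms as independent binomials with n = 20. The probability that they differ by 4 or more is 0.164, 0.226, 0.258 and 0.268 for p of 20%, 30%, 40% and 50%. For 5 or more it is 0.073, 0.119, 0.145 and 0.154. Each direction has half of this probability.

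**Step 4: what an imbalance does.** The grade effect in SD units is √(R²/(p(1 − p))). With a 5-patient imbalance (25 percentage points), p = 30% and R² = 0.10, the shift with no treatment effect is √(0.10/0.21) × 0.25 = 0.17 SD. Over p of 30% and 50%, the shift is 0.16-0.17, 0.22-0.24 and 0.27-0.30 SD for R² of 0.10, 0.20 and 0.30. The unadjusted false-positive rate, given that imbalance, is 13-14%, 15-17% and 18-20%. The adjusted rate stays near 10%.

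Now suppose a true 1.0 SD effect that lowers a marker which is higher in grade 2. For imbalances of 4 or more:

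| R² | Unadjusted, more grade 2 on metformin | Unadjusted, more grade 2 on control |
|---|---|---|
| 0.10 | 80-82% | about 97% |
| 0.20 | 73-76% | about 99% |
| 0.30 | 68-72% | about 99.5% |

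In the first of these cases, adjusted power is 92-96%.

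**Step 5: choice of adjusted test.** A van Elteren test on the four BMI-by-grade strata does worse. With 40% of patients in the upper BMI stratum and BMI not prognostic (both assumed), its power for 1.0 SD is 88-89% at R² = 0, 89.4-89.8% at 0.05 and 90.9-91.2% at 0.10. At an R² of 0.05 or less it misses the plan's own 90% criterion.

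**The case against.** The strongest reply is that nothing here is an error. A rank-sum test after randomisation is valid whatever the prognostic value of grade, its simulated type I error is 9.9-10.4% throughout, and it meets the power criterion that the plan set. That stands. A reader might infer that leaving grade out biases or invalidates the comparison. The documents do not support this: chance imbalance raises the error rate only given that an imbalance has occurred, not over the randomisation.

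A reader might also infer that power is certainly being lost. That is not supported either. Neither document gives an association between grade and any marker, entry is restricted to two grades, and the primary list covers proliferation, apoptosis and signalling markers that need not share one R². For some of them adjustment may cost up to about a point.

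Nor is a sizeable imbalance likely. It arises in roughly a quarter of trials, and the unfavourable direction in about half of those (some 13% at a 40% grade 2 share); in the opposite direction the unadjusted test gains power.

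Finally, the missing diagnosis-tissue analysis does not support the point about grade, because that tissue is not assured for every patient.

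What the reply does not answer is that the adjustment uses data already held, that its possible loss is small, and that one trial with one allocation will have to be interpreted. Meeting 90% at 1.0 SD does not settle the matter, since no marker data are given to support 1.0 SD and unadjusted power at 0.8 SD is about 77%.

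**Conclusion.** The point holds as a recommended improvement, not as a correction of an invalid analysis. The primary test ignores a baseline covariate known for every patient and also the randomisation stratum. Against an unadjusted power of about 91% for 1.0 SD, adjustment changes power by about −1 point (grade unrelated to the marker) to +5 points (R² = 0.30). At 0.8 SD the gain is about 3 to 11 points for R² of 0.10 to 0.30. It also keeps the error rate near 10%, and power at 92-96% for 1.0 SD, in the allocations where grade is unfavourably unbalanced. These sizes rest on the assumed R², the assumed grade 2 share and normal data. The absence of covariates from the plan and the availability of grade rest on the documents alone.

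**What to change.** In the analysis plan for the IHC-based primary endpoints, in both the Protocol and the SAP:

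- For tumour endpoints, make the between-arm test a rank-based ANCOVA (ranks regressed on arm, pre-study grade 1 versus 2, and BMI stratum), two-sided at 10%.
- State that the pre-study grade is used, not the post-operative one, which is recorded after treatment.
- Keep the plain rank-sum test as a sensitivity analysis.
- Do not use a van Elteren test on the four BMI-by-grade strata.
- Where diagnosis tissue exists, the marker's pre-treatment value may be added as a covariate in a supportive analysis of those patients.

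This should be fixed before the marker data are compared: in an open-label trial, an adjustment chosen after an imbalance has been seen would carry little weight. The cost is about 0.5-1 point of power for markers unrelated to grade, a change of wording in two documents and minor programming. No extra patients, visits or assays are needed.
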